4.5 Overall Survival (OS)

Overall survival, defined as the time from the date of the first dose of ribociclib to the date of death due to any cause will be analyzed using methods similar to those stated above for PFS. That is, the 25th percentile, median, and 75th percentile of survival time with corresponding 95% CIs will be provided; survival curve and survival rates at time points, such as 3, 6, 9, 12, 18, and 24 months will also be presented. Patients who are alive at the time of discontinuation/completion of the study will be censored at the last contact date (as defined in Section 2.5.7). Analyses will be based on all tumor types combined. For tumor types that have ten (10) or more patients, separate summaries will be performed by the tumor type.

Handling missing month/day in date of death

For rare cases when either day is missing or both month and day are missing for the date of death, the follow imputation rules will be implemented:

- If only day is missing, then impute maximum of [(1 mmm-yyyy), minimum of (any valid date from data base used for deriving last contact date + 1, cut-off date)].
- If both day and month are missing, then impute maximum of [(1 Jan-yyyy, minimum of (any valid date from data base used for deriving last contact date + 1, cut-off date)].

4.6 Clinical Benefit Rate by Gene Mutations

The concordance between gene mutations detected by local and central labs will be summarized on protocol pre-defined mutations. A frequency summary will be provided for summarizing clinical benefit rate per gene mutation using mutation data provided by the central lab (on protocol pre-defined mutations only) as well as local lab. The data will also be presented in a listing.

5 Safety evaluation

The assessment of safety will be based mainly on the frequency of adverse events and on the number of laboratory/ECG values that fall outside of pre-determined ranges. Other safety data (e.g. vital signs) will be considered as appropriate.

All safety outputs will use the safety set. The safety summary tables will only include “on-treatment” assessments (see the definition of “on-treatment” in Section [2.5.6](#)), i.e. those collected on or after the first date of study treatment and collected no later than 30 days after the date of last study treatment administration. The AEs started before the first dose but worsened during the treatment are also considered as ‘on-treatment’ events. All safety assessments will be listed and those collected later than 30 days after the last treatment/exposure date will be flagged.

5.1 Adverse events

5.1.1 Coding of AEs

Adverse events are coded using the MedDRA (v18.0).

5.1.2 Grading of AEs

AEs will be assessed according to the Common Terminology Criteria for Adverse Events (CTCAE) version 4.03.

The CTCAE represents a comprehensive grading system for reporting the acute and late effects of cancer treatments. CTCAE v4.03 grading is by definition a 5-point scale generally corresponding to mild, moderate, severe, life threatening, and death. This grading system inherently places a value on the importance of an event, although there is not necessarily proportionality among grades (a Grade 2 is not necessarily twice as bad as a Grade 1).

If CTCAE grading does not exist for an adverse event, grades 1 – 4 corresponding to the severity of mild, moderate, severe, and life-threatening will be used. CTCAE grade 5 (death) will not be used in this project; rather, this information will be collected on the “End of Treatment”, “30-days safety follow-up” or “Survival Information” eCRF pages.

5.1.3 General rules for AE reporting

AE summaries will include all AEs starting on or after study Day 1 (i.e. on or after the day of the first intake of study treatment) and starting no later than 30 days after the last treatment/exposure date. All AEs will be listed. AEs starting prior to study Day 1 and AEs starting later than 30 days after the last treatment/exposure date will be flagged in the listings.

AEs will be summarized by presenting the number and percentage of patients having at least one AE, having at least one AE in each body system/primary system organ class, and for each preferred term using MedDRA coding. A subject with multiple occurrences of an AE will be counted only once in the AE category.

Separate AE summaries will be presented by primary system organ class (SOC), preferred term (PT), and maximum CTC grade. A patient with multiple CTC grades for an AE will be summarized under the maximum CTC grade recorded for the event. In the summaries presented by grade, all AEs will be pooled regardless of whether they are CTC gradable or not.

Any information collected (e.g. CTC grades, relatedness to study drug, action taken etc.) will be listed as appropriate.

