### 7.1.1 Screening

For the purpose of this study, genomic profiling is not considered part of screening. This study is intended for patients who have already had genomic profiling of their tumors in a CLIA certified laboratory and have already been pre-identified to have tumors with relevant pathway activation. The results of this testing must be known prior to signing the ICF and before formal screening begins. Written informed consent must be obtained before any study specific assessments are performed, including screening. All screening evaluations must be performed as closely as possible to the beginning of treatment and never more than 28 days prior to starting study drug dose of ribociclib.

Upon signing the Informed Consent Form (ICF), a patient will be assigned a 7-digit patient number.

Patient must have archival tissue available for submission to allow for molecular testing related to pathway activation and other analyses. If the tissue is not available or is insufficient, the patient must be willing to undergo a fresh tumor biopsy to allow for this analysis. The tissue submitted will not be used to determine study eligibility. Eligibility is based on the local assessment.

An archival or fresh tumor sample may not be required if the patient has had their genomic profiling performed at the same laboratory that will be used for confirmatory analysis, and the patient consents to allow Novartis to use that to use that data as their baseline molecular analysis results.

For the purposes of enrollment, the patient's pathway activation status is based on the presence of known aberrations identified in [Section 5.2](#).

Patients who fail to start on treatment within 28 days of screening may be re-screened.

Disease assessments (per RECIST 1.1 or appropriate hematologic response criteria) must be performed within 28 days prior to enrollment and will be assessed locally by the investigator.

Information from procedures (for example imaging assessments) that may have been previously performed as part of the patient's routine disease care (prior to enrolling in the trial) is allowed to be used to satisfy inclusion criteria, if it was performed <28 days before the start of study treatment.

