#### **8.1.1 Definitions and reporting**

An adverse event (AE) is defined as the appearance of (or worsening of any pre-existing) undesirable sign(s), symptom(s), or medical condition(s) that occur after patient's signed informed consent has been obtained.

For patients who sign the ICF, all AEs will be captured in the AE eCRF from time of signature through 30 days after permanent study treatment discontinuation. For patients who fail the screening, only SAEs will be captured in the AE eCRF page.

Abnormal laboratory values or test results occurring after informed consent constitute adverse events only if they induce clinical signs or symptoms, are considered clinically significant, require therapy (e.g., hematologic abnormality that requires transfusion or hematological stem cell support), or require changes in study medication(s).

Adverse events that begin or worsen after informed consent should be recorded in the Adverse Events eCRF. Conditions that were already present at the time of informed consent should be

recorded in the Medical History eCRF. Adverse event monitoring should be continued for at least 30 days following the last dose of study treatment. Adverse events (including lab abnormalities that constitute AEs) should be described using a diagnosis whenever possible, rather than individual underlying signs and symptoms. When a clear diagnosis cannot be identified, each sign or symptom should be reported as a separate Adverse Event.

Adverse events will be assessed according to the Common Terminology Criteria for Adverse Events (CTCAE) version 4.03. If CTCAE grading does not exist for an adverse event, the severity of mild, moderate, severe, and life-threatening, corresponding to Grades 1-4, will be used. CTCAE Grade 5 (death) will not be used in this study; rather, information about deaths will be collected through a Death form.

The occurrence of adverse events should be sought by non-directive questioning of the patient (subject) during the screening process after signing informed consent and at each visit during the study. Adverse events also may be detected when they are volunteered by the patient (subject) during the screening process or between visits, or through physical examination, laboratory test, or other assessments. As far as possible, each adverse event should be evaluated to determine:

1. The severity grade (CTCAE Grade 1-4)
2. Its duration (Start and end dates)

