#### **10.5.3.1 Analysis set and grouping for the analyses**

##### **10.5.3.1.1 Adverse events (AEs)**

All adverse events recorded during the study will be summarized. The incidence of treatment-emergent adverse events (new or worsening from baseline) will be summarized by system organ class and/or preferred term, maximum severity (based on CTCAE v4.03), type of adverse event, relationship to the study treatment by treatment group. Deaths reportable as SAEs and non-fatal serious adverse events will be listed by patient and tabulated by type of adverse event and patient group.

Adverse events will be summarized by presenting the number and percentage of patients by system organ class and/or preferred term, the maximum severity (based on CTCAE v4.03) and treatment arm. Adverse events related to study treatment will also be summarized. In

addition, adverse events of related nature may be analyzed by categories regrouping the relevant preferred terms, as appropriate.

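### The SAP's rule for adverse event tables selects by start date alone, so it can leave out screening-onset events that worsen on ribociclib, which SAP Section 5 and the protocol count

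*SAP*

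**What the plan says.** Three places govern which adverse events reach the tables.

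- **SAP 5.1.3**, the specific rule for AE summaries: "AE summaries will include all AEs starting on or after study Day 1", with an upper limit of 30 days after last treatment. It adds: "AEs starting prior to study Day 1 and AEs starting later than 30 days after the last treatment/exposure date will be flagged in the listings".
- **SAP Section 5**, opening text (printed directly after Section 4.6): "The safety summary tables will only include" on-treatment assessments. It then says: "The AEs started before the first dose but worsened during the treatment are also considered as" on-treatment events.
- **Protocol 10.5.3.1.1**: the incidence of "treatment-emergent adverse events (new or worsening from baseline) will be summarized" by system organ class or preferred term, maximum severity and relationship to treatment.

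SAP 2.3, which lists changes from the protocol, covers cardiac imaging, the pooling of summaries and duration of response. It does not mention AE selection.

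**The concern.** SAP 5.1.3 makes no exception for worsening. It handles an event that began before Day 1 in the same way as one that began after the 30-day window: both are listed with a flag. A programmer who follows 5.1.3 and one who follows the opening of Section 5 could build different tables from the same data.

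The outputs at stake are those in SAP 5.1.4 and 5.1.5: all AEs, suspected-related AEs, serious AEs, AEs leading to discontinuation, AEs requiring dose adjustment or interruption, and AEs of special interest. A patient who stops ribociclib because a screening-onset event became severe could appear under the discontinuation reasons of SAP 3.3 and be absent from the table of AEs leading to discontinuation. With no control arm, an undercount has no comparator to offset it.

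**Working it through.** No formula underlies this rule and the plan gives no figure to reproduce. The check is a comparison of texts.

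**1. Can such an event exist in the data?** Yes. Protocol 8.1.1 says "all AEs will be captured in the AE eCRF from time of signature through 30 days after permanent study treatment discontinuation". Protocol 7.1.1 requires screening evaluations "never more than 28 days prior to starting study drug dose of ribociclib". AE records with a start date before Day 1 are therefore expected, from a window of at most 28 days.

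**2. Trace one event.** Suppose nausea begins at grade 1 in screening, reaches grade 3 in Cycle 2, and is kept as one record with its original start date.
- Protocol 10.5.3.1.1: worse than baseline, so summarised.
- SAP Section 5: began before dosing and worsened on treatment, so on-treatment and eligible for the tables.
- SAP 5.1.3: start date before Day 1, so flagged in the listing and not admitted to the table.

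SAP 2.5.6 says listings flag whatever is not on-treatment. The flag that 5.1.3 puts on early starts therefore marks them as off-treatment, the opposite of Section 5.

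**3. Would worsening keep the original start date?** The documents do not give the eCRF convention. They lean towards one continuing record:
- The sentence in SAP Section 5 has a purpose only if a worsened event can carry a pre-dose start date. If every worsening opened a new record, it would be redundant.
- Protocol 8.1.1 has a detected event followed to resolution, with changes in severity assessed at each visit.
- Protocol 8.2.2 has progression of a serious event reported as follow-up to the original episode.
- SAP 5.1.3 provides for one AE with several grades. That could equally mean several records under one term, so it supports the reading without deciding it.

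**4. What is outside the problem?**
- Protocol 8.1.1 sends conditions present at consent to Medical History and defines an AE to include the worsening of a pre-existing condition. One that first worsens after dosing enters as an AE beginning after Day 1 and passes 5.1.3.
- Laboratory shift tables (SAP 5.3) use the worst on-treatment value, and ECG shift tables (SAP 5.5) the worst post-baseline value. Neither uses an AE start date.

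**5. Size.** The documents give no count of events that began between consent and first dose and later worsened, so no undercount can be computed. Only the sensitivity per patient can be shown. Amendment 3 reports 106 enrolled; the Safety Set size is not stated. On a denominator of 106, each omitted patient lowers a term's incidence by 1/106 = 0.94 percentage points. The tables of most frequent AEs (at least 5%) need 0.05 × 106 = 5.3, that is 6 patients (6/106 = 5.7%; 5/106 = 4.7%). A term with a true count of 6 would leave those tables if one patient were omitted.

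**The case against.** The best defence is that the plan, read as a whole, already includes these events. SAP 5.1.3 does not say that only events starting from Day 1 are included, and Section 5 is the parent rule for all safety tables, so it could be read as adding to 5.1.3. Protocol 8.1.1 asks for a single severity grade with start and end dates for each AE, which suits a practice of opening a new record when the grade changes. Under that practice the worsened event passes 5.1.3. Safety is also descriptive, no decision rule depends on it, and every AE is listed.

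Part of this stands. The loss is conditional on eCRF practice, and its consequence is limited. The defence does not remove the conflict: start date is the sole inclusion criterion in 5.1.3, early starters are expressly sent to flagged listings, and the more specific section is the one likely to be programmed. Even if sites do open new records, the two sections still disagree.

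A reader might infer that worsened events in general disappear from the safety tables, given how many pretreated patients have fatigue or nausea at entry. The documents do not support this. Symptoms present at consent are Medical History and become new AEs when they first worsen on drug, and laboratory and ECG worsening is captured in the shift tables. A reader might also put a percentage on the undercount, but no figure in the documents yields one. In addition, a patient with another qualifying record of the same term is still counted for incidence.

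**Conclusion.** The inconsistency holds, both within the SAP (5.1.3 against Section 5) and between SAP 5.1.3 and protocol 10.5.3.1.1, and SAP 2.3 does not declare it. Its effect is confined to the AE, serious AE and special-interest tables, and to events recorded as starting between consent and first dose that later worsen without a new start date. Where that happens, the error is an understatement of incidence, of maximum grade, or of both. Its size is unknown and rests on an eCRF convention that the documents do not give. No efficacy result or stopping decision changes. It should be settled before the AE tables are programmed, as a harmonisation of a stated rule.

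**What to change.** Amend SAP 5.1.3 so that summaries include AEs that start, or increase in grade over the last grade before first dose, from Day 1 to 30 days after the last dose, counted at the worst on-treatment grade. The last pre-dose grade agrees with the general baseline definition in SAP 2.5.5. Limit the pre-Day-1 listing flag to events that did not worsen.

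State also how worsening is dated in the eCRF, by a new record or by a grade-change date. This comes first: if a record holds one grade and one start date, the amended rule cannot be derived from it without a recording convention or data queries.

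If the narrower rule is what the sponsor intends, declare it in SAP 2.3 as a departure from the protocol and delete the conflicting sentence in Section 5.

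The cost is a short SAP edit and a small programming change. AE counts may rise slightly.

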5.1.4 AE summaries

The following summary tables will be provided:

- AEs, regardless of study treatment relationship by primary SOC, PT, maximum CTCAE grade
- Most frequent ($\geq 5\%$) AEs, regardless of study treatment relationship by PT, maximum CTCAE grade
- AEs suspected to be related to the study treatment by primary SOC, PT, maximum CTCAE grade
- Most frequent ($\geq 5\%$) AEs, suspected to be related to the study treatment by PT, maximum CTCAE grade
- Serious adverse events (SAE), regardless of study treatment relationship, by primary SOC, PT, maximum CTCAE grade
- SAEs suspected to be related to the study treatment, by primary SOC, PT, maximum CTCAE grade
- Deaths on treatment by primary SOC and PT
- AEs leading to study drug discontinuation, regardless of study treatment relationship, by primary SOC, PT and maximum CTCAE grade
- AEs requiring dose adjustment or study treatment interruption, regardless of study treatment relationship, by primary SOC, PT, maximum CTCAE grade
- AEs requiring additional therapy, regardless of study treatment relationship, by primary SOC, PT, maximum CTCAE grade

In addition, subgroup analyses will be performed for all AEs and AEs suspected to be related to the study treatment.

- Age (< 65 years vs ≥ 65 years, and < 75 years vs. ≥ 75 years)
- Race (Asian, Black or African American, White and others)
- Gender (female vs. male)
- Liver metastasis (yes vs. no)
- Prior lines of chemotherapy (1, 2-3 vs. ≥ 4 lines)

AEs of interest will also be summarized. Please see Section [5.1.5](#) for the grouping details

5.1.5 AEs of special interest

AE of special interest (AESI) consists of adverse events for which there is a specific clinical interest in connection with ribociclib treatment (i.e. where ribociclib may influence a common mechanism of action responsible for triggering them) or adverse events which are similar in nature (although not identical).

Each of these AESI uses MedDRA categories (Standard MedDRA Query [SMQ], Novartis MedDRA Query [NMQ], High Level Group Term [HLGT], etc.) to group preferred terms for which there is a specific clinical interest. One AESI can be defined by one or several MedDRA categories. These AESIs are defined in the current version of the ribociclib Safety profiling plan/ ribociclib Case Retrieval Strategy (CRS) document.

The number and percentage of patients will be reported by AESI and by preferred term. Groupings are displayed as below –

- Hepatobiliary toxicity
- QTc prolongation
- Nausea, emesis
- Diarrhea
- Pneumonitis, interstitial lung disease
- Anemia
- Thrombocytopenia
- Haematopoietic cytopenias affecting more than one type of blood cell
- Leukopenia and neutropenia
- Renal Toxicity

Additional AESIs may be reported if there are any updates to the CRS at the time of the analyses.

The number and percentage of patients will be reported by AESI, by MedDRA term, by PT, maximum CTCAE.

These analyses will be repeated in subgroups specified in Section [5.1.4](#), for the following AESIs:

- Leukopenia and neutropenia
- QT prolongation
- Hepatobiliary toxicity

5.2 Deaths

The number and percentage of patients who died within 30 days of the last dose will be summarized with cause of deaths.

A patient listing of all deaths with recorded principal cause of death (if available) will also be provided. All patients in FAS who died will be included, with deaths that are within 30 days of the last dose noted.

5.3 Laboratory evaluations

Laboratory assessment will be collected at screening and post baseline (at scheduled visits outlined in the protocol or as clinically indicated). The collected laboratory values will be converted into standard units and the severity grade will be calculated using CTCAE v4.03. A severity grade of 0 will be assigned when the value is within normal limits. For laboratory parameters where severity grades are determined both through normal limits and absolute cut-offs, in the unlikely case that a local laboratory normal range overlaps into the higher (i.e., non-zero) CTCAE grade, the laboratory value will still be taken as within normal limits and assigned a CTCAE grade of zero.

Abnormal on-treatment laboratory values will be summarized using shift tables (from baseline to any abnormal laboratory value post baseline) by each laboratory parameter at its worst severity grade. The number and percentage of patients with abnormal laboratory values will be presented by CTCAE grade for each laboratory parameter that is CTCAE gradable. For laboratory parameters where CTCAE grades are not defined, shift tables using the low/normal/high/(low and high) classification to compare baseline to the worst on-treatment value will be provided. Listings of all laboratory values (blood chemistry, hematology/coagulation parameters separately) in chronologic order will be provided for each laboratory parameter. Laboratory values collected more than 30 days after study treatment discontinuation will be flagged in the listing. Separate listings will also be provided for notable laboratory abnormalities (i.e., grade 3 or 4 laboratory toxicities post start of study treatment for CTC gradable parameters, or abnormal laboratory values for non-CTC gradable parameters). In addition, other lab tests such as those for urinalysis and pregnancy will be listed separately.

Patients' hepatic toxicity will be evaluated for on-treatment liver parameter values. The worst case assessments are used for the analyses. The number and percentage of patients who met the following categories of the criteria will be presented.

- ALT > 3xULN, ALT>5xULN, ALT>8xULN, ALT>10xULN, ALT>20xULN, separately
- AST >3xULN, AST>5xULN, AST>8xULN, AST>10xULN, AST>20xULN, separately
- ALT>3xULN or AST>3xULN, ALT>5xULN or AST>5xULN, ALT>8xULN or AST>8xULN, ALT>10xULN or AST>10xULN, ALT>20xULN or AST>20xULN, separately
- TBILI>ULN, TBILI>2xULN, separately
- ALP>1.5xULN, ALP>2xULN, ALP>3xULN, ALP>5xULN, ALP>8xULN, ALP>10xULN, separately
- (ALT>3xULN or AST>3xULN) and TBILI>ULN, (ALT>5xULN or AST>5xULN) and TBILI>ULN, (ALT>8xULN or AST>8xULN) and TBILI>ULN, (ALT>10xULN or AST>10xULN) and TBILI>ULN, (ALT>20xULN or AST>20xULN) and TBILI>ULN, separately
- (ALT>3xULN or AST>3xULN) and TBILI>2xULN, (ALT>5xULN or AST>5xULN) and TBILI>2x ULN, (ALT>8xULN or AST>8xULN) and TBILI>2x ULN,

(ALT>10xULN or AST>10xULN) and TBILI>2x ULN, (ALT>20xULN or AST>20xULN) and TBILI>2x ULN, separately

- (ALT>3xULN or AST>3xULN) and TBILI>=2xULN and ALP<2xULN

Note: ALT = Alanine Aminotransferase; AST =

